10.10.2 Listeriosis and Listeria Infection-Identification and Management

A person with wild type (*wt*) listeriosis usually presents with fever and muscle aches, sometimes preceded by diarrhea or other gastrointestinal symptoms. Almost everyone who is diagnosed with listeriosis has an "invasive" infection, in which the bacteria spread beyond the gastrointestinal tract. The symptoms vary with the infected person. Pregnant women typically experience fever and other non-specific symptoms, such as fatigue and aches. However, infections during pregnancy can lead to miscarriage, stillbirth, premature delivery, or life-threatening infection of the newborn. In people other than pregnant women, symptoms can include headache, stiff neck, confusion, loss of balance, and convulsions in addition to fever and muscle aches. Listeriosis can present in different ways. In older adults and people with immunocompromising conditions, septicemia and meningitis are the most common clinical presentations.[58] Subjects may need immediate evaluation with a brain CT scan or MRI and a lumbar puncture with the analysis of spinal fluid to rule out meningitis.

For symptomatic subjects, diagnosis is confirmed only after isolation of *Lm* from a normally sterile site, such as blood or spinal fluid (in the setting of nervous system involvement), or amniotic fluid/placenta (in the setting of pregnancy). Stool samples are of limited use and are not recommended. *Lm* can be isolated readily on routine media, but care must be taken to distinguish this organism from other Gram-positive rods, particularly diphtheroids. Selective enrichment media improve rates of isolation from contaminated specimens. You can expect that the cultures will take approximately 1-2 days for growth. Importantly, a negative culture does not rule out infection in the presence of strong clinical suspicion. Serological tests are unreliable, and not recommended at the present time [58].

Listeriosis is treated with a wide range of antibiotics. In preclinical studies, *wt-Lm* and ADXS11-001 are susceptible to the lowest tested concentration of the following antimicrobial agents: ampicillin, amoxicillin/K clavulanate, ciprofloxacin, erythromycin, gentamicin, penicillin, tetracycline, trimethoprim/sulfamethoxazole and vancomycin (IV). ADXS11-001 is resistant to both streptomycin and chloramphenicol.

10.10.3 Management and Surveillance of Listeria during Study Participation

In the event a subject experiences a persistent fever lasting 72 hours after receiving study treatment then the oral antibiotic regimen will be replaced by broad spectrum IV antibiotic treatment. If symptoms consistent with sepsis occur close to ADXS11-001 administration or at any time after ADXS11-001 administration, immediate medical attention must be sought. A microbial culture will be taken to identify the agent of sepsis and antibiotic sensitivity testing should be performed to confirm susceptibility. An infectious disease consult should be obtained for further management of these subjects.

All subjects will receive a 6-month course of an oral antibiotic regimen as a prophylactic measure approximately 72 hours following the completion of the last dose of ADXS11-001 treatment or at the time of study discontinuation. This additional safety measure is intended to eradicate *Lm* from the body.

Lm surveillance monitoring will also be initiated following the completion of the last dose of ADXS11-001 treatment or at the time of study discontinuation. This monitoring will include obtaining a blood sample for CBC, comprehensive metabolic panel (CMP), including CRP and ESR, and blood cultures for the detection of *Listeria*. Testing will be performed on all subjects who have received at least 1 dose of ADXS11-001 and occur 3 months(+/- 2 weeks), 6 months(+/- 3 weeks), 9 months(+/- 1 Month), 12 months(+/- 1 Month), and every 4 months(+/- 1 Month) for year 2 and year 3 postoperatively.

Should a diagnosis of listeriosis be made at any point after treatment with ADXS11-001 is completed, immediate and intensive IV antibiotic treatment (ampicillin +/- gentamycin or other IV antibiotic regimen as indicated) is required. An infectious disease consult should be obtained. Based on each individual subject's case and at the discretion of the treating physician, the removal of any foreign medical object that has been present since treatment with ADXS11-001 was initiated may be warranted. It is extremely important that the Investigator, his/her research staff, other healthcare providers involved in the care of the subject as well as each subject participating in this study are educated and made aware of the signs and symptoms of listeriosis and the potential for delayed listeremia/listeriosis. Educational materials for the Investigator, research staff, health care providers and subjects will be prepared and educational training performed.

10.10.4 Potential for delayed/late *Listeria* infection:

ADXS11-001 has been attenuated by ≥ 4 logs in comparison to the wild-type (wt)-*Lm*. ADXS11-001 is cleared by SCID mice lacking a functioning cellular immune system, as well as by gamma interferon knockout mice lacking adaptive immunity. ADXS11-001 has been shown to be nonpathogenic in mouse models. In a Phase 1 clinical study, in the absence of antibiotics, *Lm* was rapidly cleared from the blood. No *Lm* was detected in the blood, urine or feces of any subject beyond 48 hours post-dosing and at the highest dose of ADXS11-001 tested (1×10^{10} CFU)⁵².

11 TRANSORAL SURGERY FOR OROPHARYNGEAL CANCER

1. Patients have previously been determined by an attending Head and Neck surgeon and the multidisciplinary tumor board at each site, to be eligible for transoral resection.
2. Standard-of-care transoral surgery with intent to perform complete resection of the primary tumor will be performed according to our previously described methods⁵⁰. In brief: surgery will include transoral robotic resection or transoral laser resection of the tumor with negative intraoperative frozen section margins; in selected cases it may be appropriate to remove the tumor with hand-held electrocautery under direct vision. Appropriate reconstruction will be performed at the time of tumor resection as deemed necessary by the operating surgeon.
3. Selective neck dissection of levels II-IV will be performed routinely ipsilateral to the primary tonsillar tumors. Bilateral selective neck dissection of levels II-IV will be performed for all tongue base tumors. Additional levels (i.e. I, V) will be performed at the discretion of the operating surgeon if indicated on the size and location of the primary tumor. N+ patients will undergo a simultaneous appropriate therapeutic neck dissection.

11.1 POSTOPERATIVE ADJUVANT THERAPY AND CLINICAL FOLLOW-UP

1. Adjuvant radiation therapy or chemoradiation will be given to appropriate patients based on preoperative and pathological risk factors as per standard-of-care. Participation in this trial will in no way alter the decision to provide post-surgical radiation or chemoradiation. While there is some leeway based on clinical judgment, standard criteria for adjuvant therapy include: positive surgical margin; lymphovascular invasion (LVI); perineural

invasion (PNI); extracapsular spread (ECS) of lymph node metastases or matted lymph nodes; low (level IV) cervical lymph nodes; >2 positive lymph nodes. These criteria are fairly standard across many institutions. If adjuvant therapy is indicated, therapy usually begins 4 to 6 weeks after surgical resection.

2. Patients will undergo routine post-treatment clinical follow-up, which usually involves monthly visits for the first year and q2-3 month visits in the second year following treatment. Imaging is obtained at the discretion of the treatment team, but is generally obtained no less than q 3 months for the first 2 years after treatment.
3. Assessment of disease status (no evidence of disease / NED; recurrent disease; second primary upper aerodigestive tumor; other second primary cancer) is performed by the attending surgeon at each follow-up appointment, and recorded in the electronic medical record (EMR).

12.0 SCHEDULE OF BLOOD AND SAMPLE COLLECTION

12.1 TREATMENT GROUP

1. The day of the first dose of vaccination will be considered “day 1”.
2. Standard-of-care pre-treatment tumor biopsy will be performed in a timely fashion for those patients without a prior biopsy, whose prior biopsy is inadequate for clinical planning, or for whom prior biopsy material adequate for immunophenotyping by immunohistochemistry (IHC) is not available.
3. Initial blood draw (Draw 1) will be obtained prior to the first vaccination usually during screening visit.
4. Draw #2 will be performed on the day of the first vaccination (e.g. day 1) before vaccine infusion.
5. Draw #3 will be performed on the day of the second vaccination (day 15) before vaccine infusion.
6. Surgery, and harvest of tumor and TIL, will be performed on day 35 +/- 7 days following entry into the study and baseline blood draw.
7. Draw #4 will be performed preoperatively, on the day of surgery prior to induction of anesthesia, or up to 72 hours prior to the surgery.
8. Draw #5 will be performed 3 weeks (+/- 1 week) after surgery.
9. Draw #6 will be performed 6 weeks (+/- 1 week) after surgery, before radiation.
10. Draw #7 will be performed 3 months (+/- 3 weeks) post-surgery.
11. Draw #8 will be performed 6 months (+/- 3 weeks) post-surgery.
12. Draw #9 will be performed 12 months (+/- 4 weeks) post-surgery.

12.1.1 LISTERIA SURVEILLANCE MONITORING BLOOD DRAW: Up to 45 ml of additional blood will be collected for safety follow up testing as *Listeria* surveillance monitoring. It will include CBC, CMP, including CRP and ESR and blood cultures for the detection of *Listeria*.

Patients in the control group will NOT undergo additional blood draw or monitoring. These blood draws will be performed at 3 months(+/- 2 weeks), 6 months(+/- 3 weeks), 9 months(+/- 1 Month), 12 months(+/- 1 Month), and every 4 months(+/- 1 Month) for year 2 and year 3 as mentioned in schedule above.

12.2 OBSERVATIONAL GROUP

1. The day of screening will be considered “day 0”. Initial blood draw (Draw 1) will be obtained at screening.
2. Standard-of-care pre-treatment tumor biopsy will be performed in a timely fashion for those patients without a prior biopsy, whose prior biopsy is inadequate for clinical planning, or for whom prior biopsy material adequate for immunophenotyping by immunohistochemistry (IHC) is not available.
3. Draw # 2: Observational patients will NOT undergo this blood draw.
4. Draw # 3: Observational patients will NOT undergo this blood draw.
5. Draw #4 will be performed preoperatively, on the day of surgery prior to induction of anesthesia, or up to 72 hours prior to surgery.
6. Draw #5 will be performed 3 weeks (+/- 1 week) after surgery.
7. Draw #6 will be performed 6 weeks (+/- 1 week) after surgery, before radiation.
8. Draw #7 will be performed 3 months (+/- 3 weeks) after surgery.
9. Draw #8 will be performed 6 months (+/- 3 weeks) after surgery.
10. Draw #9 will be performed 12 months (+/- 4 weeks) after surgery.

12.3 COLLECTION AND PROCESSING OF PERIPHERAL BLOOD SAMPLES

1. Baseline blood samples will be collected either immediately after consent or prior to the first vaccination. Samples will be collected at baseline, on the day of surgery (following two rounds of vaccination), and according to the schedule described above.
2. At each collection, peripheral blood samples (eight 7mL tubes, 56 mL total) will be withdrawn by a clinical research coordinator, a medical assistant or a clinic nurse and promptly transported to the designated laboratory for processing. Immediately prior to drawing blood, the person in charge of the procedure will verify the subject's identity. Immediately after the blood has been collected, a label containing the appropriate subject identification number and the subject's initials is to be affixed to the vial.
3. Serum will be obtained by centrifugation, and stored in 250uL aliquots at -80°C. Whole blood will be processed over a Ficoll gradient to obtain PBMC, and PBMC will be washed, counted, aliquotted and frozen in DMSO-containing freezing medium prior to long-term storage in liquid nitrogen. All tubes will bear self-adhesive labels that clearly identify the trial code, the patient number, the patient initials, and the visit number. Sterile technique will be maintained throughout so that viable cells may be cultured and assayed after thawing.

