6.0 RESEARCH PLAN AND METHODS

This is a window of opportunity single-arm phase II clinical trial in which a group of surgically-resectable HPVOPC patients will receive the ADXS11-001 vaccine before standard-of-care transoral surgical resection. Vaccinated patients will be enrolled according to a Simon's two-stage design, with an initial cohort of 9 patients enrolled before preliminary analysis, and a

subsequent cohort of 13 patients enrolled if statistical criteria are met. To better understand the immunology of un-vaccinated HPVOPC patients, we will also enroll an optional observational group of up to 10 patients with the same characteristics who will undergo transoral resection without vaccination. We will collect, process and store tumor specimens, tumor-derived leukocytes, and serum and cellular components of peripheral blood, at different time points from study patients prior to analysis of batched samples at a later date once the specimens from 5 or more patients are available.

6.1 SCHEME:

[figure not shown]

Figure 2. Flow diagram for clinical trial of ADXS11-001 therapeutic HPV vaccine in HPV+ OPC patients. OPSCC – oropharyngeal squamous cell carcinoma. XRT – radiation therapy.

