8.6 Following entrance into the study, appropriate patients will be assigned to the vaccine arm by the local site PI. This group will be compared with an observational group of similar patients that will be treated with transoral surgery without vaccination during the same period of time. Since the design of this study is to compare patients' pre- and post-treatment assay results rather than results from vaccinated versus unvaccinated patients, assignment to treatment or observational group will not be randomized. Rather we will offer enrollment in the observational group to patients who do not wish to receive the vaccine but are willing to enroll in the observational portion of this trial.

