12.5 IMMUNOPHENOTYPING AND CHARACTERIZATION OF HPV-SPECIFIC T CELL RESPONSES

1. Following purification from whole blood or tumor, mononuclear cells will be cultured 48 hours in the presence or absence of pools of 15-20-mer overlapping peptides encompassing the full-length HPV16 E6 and E7 antigens, or control (CMV, EBV and Flu virus) peptide mixtures.
2. After 48 hrs of stimulation, an aliquot of supernatant from the culture will be harvested and frozen at -80°C for future studies of cytokine production.
3. E6/E7-specific T cell responses will be determined by ELISPOT, flow-cytometry for intracellular IFN-γ staining, or other comparable method. In brief, staining for T cell surface markers (CD3, CD4, CD8) with labeled antibodies is performed prior to fixation/permeabilization of cells. Fix/permed cells are then stained with labeled antibody to IFN-γ, a marker of activated cytotoxic T cells. Multicolor flow cytometric analysis is then performed on an LSR II flow cytometer.
4. Additional flow cytometry staining panels to characterize NK cells (CD56), T cell activation and exhaustion markers (granzyme, perforin, CTLA-4, PD-1), regulatory T cell (CD127, CD25), and myeloid populations (CD11c, CD11b, CD33, HLA-DR) will be used to perform multi-dimensional immunophenotyping of effector and regulatory cell populations.

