17.1 DATA CONFIDENTIALITY

All efforts will be made to ensure patient confidentiality and assurance of HIPAA compliance. Immediately after obtaining any specimens and microscopic images, subjects will be assigned a protocol specific unique code that will be used for all further data management. A list matching the patient medical record number to the protocol specific unique code will be kept in a locked cabinet in the office of the site PIs. The names of the patients will not be released to any outside organizations or to persons not involved with the study. They will not be revealed in written reports or publications detailing the research findings. All electronic data with patient identifying information will be maintained on password-protected computers at the respective institution. Use of portable media devices (external hard drives, USB drives, etc.) will be discouraged; if use of portable media devices is required for transfer of data, these devices are to be password protected and encrypted.

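### No masked or recoded reading of pre- and post-vaccine blood samples is specified, although the primary endpoint is a two-fold T-cell rise in a single-arm trial and the prescribed storage label shows the visit number

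*Combined protocol and SAP*

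**What the plan says.** - **Design.** Section 6.0 describes a "window of opportunity single-arm phase II clinical trial". Section 8.6 says that "assignment to treatment or observational group will not be randomized", and that the comparison of interest is each patient before and after treatment.
- **Endpoint.** Under section 16.0(a), a patient is a responder if the background-subtracted E6 or E7 response in blood reaches twice baseline. If there was no baseline response, the threshold is twice the average nonspecific background. Section 16.0(c) counts a response at surgery or at 3 or 6 weeks after it.
- **Assay.** Section 12.5 says "E6/E7-specific T cell responses will be determined by ELISPOT", by intracellular IFN-γ flow cytometry, or by a comparable method. For flow cytometry it adds: "Multicolor flow cytometric analysis is then performed on an LSR II flow cytometer". It gives no gating or well-exclusion rules, and does not say who reads the assay or what identifier the reader sees.
- **Labels.** At the draw, "a label containing the appropriate subject identification number and the subject's initials is to be affixed to the vial"; the visit is not listed there. For the stored serum and PBMC tubes, section 12.3 item 3 requires: "All tubes will bear self-adhesive labels that clearly identify the trial code, the patient number, the patient initials, and the visit number".
- **Timing.** Section 6.0 has samples stored "prior to analysis of batched samples at a later date once the specimens from 5 or more patients are available".
- **Coding.** Section 17.1 provides that "subjects will be assigned a protocol specific unique code that will be used for all further data management". This is a code per subject, for confidentiality. It does not hide the visit.

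**The concern.** The primary analysis compares samples from the same patient at different visits. A tendency to read later samples more generously would enter the responder count directly, and no concurrent arm in the decision rule could cancel it.

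The plan leaves some room for judgement. The platform is not fixed, the background used when baseline is negative is given only approximately, and rules for gates and wells are not stated. Two antigens at three eligible draws give up to 2 × 3 = 6 readings, any one of which can make a patient a responder.

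At stage 1 a single patient (5 or 6 of 9) separates stopping from continuing. Bias that enters at reading cannot reliably be removed afterwards, so the safeguard belongs in place before the first batch is run.

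**Working it through.** **1. Is masking provided anywhere?** Section 12.3 sets labels for storage. Section 12.5 goes from purified cells to stimulation, staining and analysis with no recoding step. Section 16.0 defines the call and the averaging of replicates. Section 17.1 codes the subject, not the visit. None of them masks the time point, randomises run order or requires readings to be locked first. The visit number is thus visible to anyone handling a stored tube that has not been recoded.

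**2. Reproduce the plan's own figures.** Inputs from section 16.0(c): 9 + 13 = 22 patients; stop at 5 or fewer of 9; uninteresting rate 50%, target 75%; success if more than 14 of 22 respond. Section 16.0(e) states type I error 10%, power 80.7%, early stopping 75% and expected size 13.

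P(success) = Σ over x = 6 to 9 of P(Bin(9, p) = x) × P(Bin(13, p) ≥ k − x), where k is the number of responders required.

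At p = 0.5 the stage 1 probabilities for x = 6, 7, 8, 9 are 84, 36, 9 and 1 over 512. The stage 2 tails for at least 9, 8, 7, 6, 5 of 13 are 1093, 2380, 4096, 5812 and 7099 over 8192.

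- k = 15 (the rule as written): (84×1093 + 36×2380 + 9×4096 + 1×5812) / (512×8192) = 220168 / 4194304 = 5.2%. Power at 75% is 75.6%.
- k = 14: (84×2380 + 36×4096 + 9×5812 + 1×7099) / 4194304 = 406783 / 4194304 = 9.7%. Power is 80.7%.
- Early stopping: 1 − 130/512 = 74.6%. Expected size: 9 + 13 × 130/512 = 12.3.

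The stated error and power match 14 or more, not the written more than 14. That is a separate discrepancy for the sponsor to reconcile; both rules are shown below.

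**3. Illustrate what misreading could cost.** Let m be the share of true non-responders called responders, with no misreading in the other direction. At a true rate of 50% the observed rate is p = 0.5 + 0.5m. **The values of m are assumptions; the documents give none.**

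| m | observed rate | false positive conclusion, 15 or more of 22 (as written) | 14 or more of 22 |
|---|---|---|---|
| 0 | 50% | 5.2% | 9.7% |
| 2% | 51% | 6.3% | 11.3% |
| 5% | 52.5% | 8.2% | 14.0% |
| 10% | 55% | 12.1% | 19.4% |
| 20% | 60% | 23.7% | 33.3% |

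For scale, if all 22 patients are treated, m = 10% is 22 × 0.5 × 0.10 = 1.1 patients; m = 2% is 0.22 of a patient.

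**The case against.** The strongest reply is that a visit number on a storage tube is ordinary traceability, and a fold-change endpoint needs it. The documents do not say that readers work from these labels, nor do they exclude recoding after thawing; a laboratory procedure outside the protocol may cover it. This stands. A reader might infer that the laboratory staff know the time point, or that the label wording is itself an error. The text supports neither. What it supports is that a masking step is absent.

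Second, the plan does limit discretion: unstimulated cultures and viral control peptides (12.5), background subtraction and averaging of two baselines where available (16.0(a)), three replicates handled identically at each draw (16.0(c)), and a numeric cut-off. If the optional observational group is enrolled and assayed the same way, its draws 1 and 4 to 9 could reveal drift linked to visit. These are real strengths, but none hides the time point, and the observational group is outside the decision rule.

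Third, the table would look the same for any upward bias, and at m = 2% the effect is about one percentage point. This also stands: the figures show sensitivity and do not estimate reader bias.

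Other tempting extensions fail. Section 12.4 repeats the label wording, but the primary endpoint is in peripheral blood and tumour-infiltrating cells are harvested only at surgery, so there is no pre/post pair to unmask. Initials on a tube reveal nothing about timing. Set against section 17.1 they raise at most a privacy question, since that section does not forbid initials as a second specimen identifier.

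**Conclusion.** The point holds as an omission. The protocol specifies no masked or recoded reading of pre- and post-vaccine blood samples, and the one label it prescribes for stored PBMC shows the visit. Followed as written, the plan permits visit-aware reading of an uncontrolled primary endpoint.

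The size is unknown. Under assumed one-way misreading of 2% to 20% of non-responders at a true 50% rate, the chance of a false positive conclusion under the written rule runs from 6.3% to 23.7%, against 5.2% with none. A reader might take the upper figures as the trial's actual error rate. They are not: they depend wholly on the assumed rate, and the documents give no assay reproducibility data. The case for change rests on how little it costs to close the gap, not on a demonstrated bias.

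**What to change.** Leave the storage labels in 12.3 as they are, for traceability, and add to 12.5:

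- Before assay, each thawed PBMC aliquot receives a random code that hides patient and visit. Plates and cytometry files carry only this code.
- All of a patient's primary-endpoint time points (draws 1 and 2 before the first infusion, draw 4 before surgery, draws 5 and 6 after it) are run in the same batch in coded order, where the timing of the stage 1 analysis permits.
- Gates, well exclusions and spot counts are locked before existing data-management staff release the key for the fold-change calculation.

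Cost: a code list, a tracking log so that the right baseline aliquots enter each batch, and a small risk of sample swaps, which the log should be designed to catch. No extra blood, assay or reader is needed. The sample size and decision rules do not change. Because the samples are frozen and batched anyway, no clinical decision is delayed. Masking the immunohistochemistry slides is an optional extra that bears only on the exploratory aim.
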